**Table 8-1 Assessment and Procedures Schedule (Baseline to 18-week safety follow up)**

Visit Day	-1 (0-24 hrs prior to randomization) 	1	2	Every day during hospitalization until Day 29 or discharge (whichever is earlier)	15 	29 or Day of Discharge 	Day 57  (±7 days)	127  (±7 days)/ End of Study
Informed consent (including optional genetic ICF and assent if applicable) 	x							
Inclusion/Exclusion criteria	x	x 						
Demographics / medical history	x							
SARS-CoV-2 virus testing (local labs)	x 	Record all testing, if obtained						
SARS-CoV-2 nasopharyngeal samples (central lab)	x					x		
Vital signs: Heart rate, Respiratory rate, Oxygen saturation or PaO 2 /FiO 2 , Systolic/diastolic blood pressure, Body temperature 	x	x 	x	x	x	x		
Height, weight	x							
Physical exam 		s 	s		s	s	s	
Clinical status evaluation with 9-point ordinal scale (e.g. oxygen requirement, invasive/non-invasive mechanical ventilation, additional organ support)		x 	x	x	x	x	x	x
Hematology (local labs)	x		x	x (every other day e.g., Days 3, 5, 7, etc.)	x	x	x	
Clinical chemistry, CRP, ferritin, d-dimer (local labs)	x		x	x (every other day e.g., Days 3, 5, 7, etc.)	x	x	x	
Pregnancy test  (local labs)	s					s	s	s
Chest x-ray or CT scan 	x	Record all pulmonary imaging if obtained						
ECG (local)	s		s			s		
Adverse events	x	x 	x	x	x	x	x	x
Prior/concomitant medications/non-drug therapy (i.e. oxygen)	x	x 	x	x	x	x	x	x

Visit Day	-1 (0-24 hrs prior to randomization) 	1	2	Every day during hospitalization until Day 29 or discharge (whichever is earlier)	15 	29 or Day of Discharge 	Day 57  (±7 days)	127  (±7 days)/ End of Study
Randomization		x						
Study drug administration		x 						
Days from onset of symptoms to study treatment		x 						

X = assessment to be recorded in the clinical database or received electronically from a vendor

[figure not shown]
S = assessment to be recorded in the source documentation only.

1. After informed consent is obtained (or assent if applicable), baseline measurements should be collected between 0 to 24 hours prior to canakinumab/placebo dose, unless otherwise specified.

2. If patient is discharged prior to Day 29, then all assessments listed for Day 29 should be conducted on the Day of Discharge. Visits at Days 15, 29, 57 and 127 should be conducted via phone for patients who were discharged prior to the visit (+/- 3 days). These phone visits should only collect Clinical status evaluation with 9-point ordinal scale, Adverse events, Concomitant medications, [redacted] whereas vital signs, physical exam, laboratory tests (including pregnancy test), [redacted] will not be conducted. If the patient remains hospitalized, however, all assessments noted in the table should be conducted on the visit day noted.

Visit Day	-1 (0-24 hrs prior to randomization) 	1	2	Every day during hospitalization until Day 29 or discharge (whichever is earlier)	15 	29 or Day of Discharge 	Day 57  (±7 days)	127  (±7 days)/ End of Study

3. Informed consent must be signed (within 0-48 hours prior to randomization) and prior to any study-related procedures, unless otherwise noted or previously conducted during hospitalization.
 
4. All baseline (Visit Day 1) assessments must have been conducted prior to dosing with canakinumab (except Days from onset of symptoms to study treatment and [REDACTED]).
 
5. Vitals signs should be recorded at a consistent time once each day for a patient (i.e. morning, afternoon or evening) and upon significant clinical changes. Respiratory rate and oxygen saturation only if not on mechanical ventilation, or PaO2/FiO2. After Day 1, if patient is receiving supplemental oxygen (not on invasive ventilation), then oxygen flow rate and/or FiO2 and oxygen saturation to be collected.
 
6. A complete physical examination will be performed for baseline, for remaining time points; targeted physical examination, per investigator discretion, and may be performed.
 
7. Pregnancy test: only for females of childbearing potential, serum pregnancy test (serum hCG) will be performed at baseline visit. Urine or serum pregnancy test to be performed at other visits, if hospitalized.
 
8. Results confirming positive SARS-CoV-2 virus by PCR or by other approved diagnostic methodology available within 7 days and chest x-ray or CT scan within 5 days prior to randomization may be used for eligibility.
 
9. Canakinumab may be dosed immediately after obtaining all baseline measurements and confirming eligibility.
 
[REDACTED]
 
[REDACTED]
 
[REDACTED]
 
13. Unscheduled visits are permitted after discharge, as needed.
								

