## 2 Objectives and endpoints

**Table 2-1 Objectives and related endpoints**

Objective(s)	Endpoint(s)
Primary Objective To demonstrate the benefit of canakinumab + standard of care (SOC) in increasing chance of survival without ever requiring invasive mechanical ventilation among patients with COVID-19-induced pneumonia and CRS	Endpoint for primary objective: Clinical response, defined as survival without ever requiring invasive mechanical ventilation from Day 3 (inclusive) up to Day 29 (inclusive).
Secondary Objective(s) To demonstrate the benefit of canakinumab in reducing 4-week case fatality rate (CFR) among patients with COVID-19-induced pneumonia and CRS regardless of other subsequent clinical interventions	Endpoint(s) for secondary objective(s): COVID-19-related death during the 4-week period after study treatment
To evaluate change in clinical serologic measurements related to CRS in COVID-19 patients with pneumonia	

• Adjusted geometric mean ratio to baseline overtime up to Day 29 in the following clinical chemistry measurements:

• CRP

• Serum ferritin

• D-dimer

To evaluate safety of canakinumab in patients with COVID-19-induced pneumonia and CRS	Number of participants with Adverse Event (AE), serious adverse events (SAE), clinically significant changes in laboratory measures, and vital signs

Objective(s)	Endpoint(s)

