#### **Chemistry**

BUN/urea, creatinine, total bilirubin, direct bilirubin, aspartate aminotransferase (AST), alanine aminotransferase (ALT), alkaline phosphatase, gamma-glutamyl transpeptidase, lactate dehydrogenase, sodium, potassium, chloride, calcium, bicarbonate, phosphorus, total protein, albumin, glucose, uric acid will be measured according to the assessment schedule in [Table 8-1](#). If a given test is not available locally, this should be documented on the eCRF.

[figure not shown]
Additional markers of inflammation: CRP, ferritin, and d-dimer should be collected in accordance with [Table 8-1](#).

In the case where a laboratory range is not specified by the protocol, but a value is outside the reference range for the laboratory at screening and/or initial baseline, a decision regarding whether the result is of clinical significance or not shall be made by the Investigator (in consultation with the sponsor) and shall be based, in part, upon the nature and degree of the observed abnormality. In all cases, the Investigator must document in the source documents, the clinical considerations (i.e., result was/was not clinically significant and/or medically relevant) in allowing or disallowing the participant to continue in the study.

All patients with laboratory tests containing clinically significant abnormalities should be followed until the values return to within the normal ranges or until a clinical explanation is identified, even after study medication has discontinued.

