### **Clinical laboratory evaluations**

Laboratory data will be summarized by treatment and visit.

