## 2.8.2    **Laboratory data**

Laboratory tests will be conducted by local lab. Clinically significant abnormal results will be reported as adverse events and included in the AE summaries; however the following liver enzyme testing results will be entered into the clinical database:

- Alanine aminotransferase (ALT)
- Aspartate aminotransferase (AST)
- Total bilirubin (TBIL) / Direct bilirubin
- Alkaline phosphatase (ALP)

Number (%) of newly occurring liver enzyme abnormalities, as listed below, at any time during post-treatment will be provided. A newly occurring event is when a patient not meeting a given criterion at baseline but meeting the corresponding criterion during post-baseline.

- ALT or AST  $> 3.0x, 5.0x, 10.0x, 20.0x$  ULN
- ALP  $> 1.5x$  ULN
- TBIL  $> 1.5x, 2.0x$  ULN
- ALT or AST  $> 3.0x$  ULN & TBIL  $> 1.5x$  ULN
- ALT or AST  $> 3.0x$  ULN & TBIL  $> 2.0x$  ULN

The last two criteria on the list are based on the maximum post-baseline ALT, AST, and TBIL.

An eDISH plot on the maximum post-baseline ALT value relative to the ULN and TBIL value relative to the ULN will also be provided at log-log scale.

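### The protocol has all clinical chemistry recorded and summarised by arm and visit, but SAP 2.8.2 names only five liver tests for entry, so 13 of 19 analytes, including creatinine, have no comparison of values in the readable SAP

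*Protocol*

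**What the plan says.** **Protocol.** Table 8-1 has two recording codes. X means "X = assessment to be recorded in the clinical database or received electronically from a vendor"; the alternative is "S = assessment to be recorded in the source documentation only". The row that holds clinical chemistry together with CRP, ferritin and D-dimer carries X wherever it is scheduled: Day -1, Day 2, every other day in hospital, Day 15, Day 29 or discharge, and Day 57. The source-only code is used for the physical examination, the ECG and the pregnancy test.

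Section 8.4.1.2 lists the panel: "BUN/urea, creatinine, total bilirubin, direct bilirubin, aspartate aminotransferase (AST), alanine aminotransferase (ALT), alkaline phosphatase, gamma-glutamyl transpeptidase, lactate dehydrogenase, sodium, potassium, chloride, calcium", and then uric acid, glucose, albumin, total protein, phosphorus and bicarbonate. It adds: "If a given test is not available locally, this should be documented on the eCRF". Section 11.1 has site staff enter into the eCRF what Table 8-1 defines. Section 12.5.3 states, with no limit to particular analytes, that "Laboratory data will be summarized by treatment and visit". The safety endpoint in Table 2-1 includes "clinically significant changes in laboratory measures, and vital signs".

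**SAP.** Section 2.8.2 says that clinically significant abnormal results from the local laboratory are reported as adverse events and counted in those summaries; "however the following liver enzyme testing results will be entered into the clinical database". The list that follows is ALT, AST, total/direct bilirubin and ALP. These are analysed as newly occurring abnormalities at multiples of the upper limit of normal, plus an eDISH plot. Elsewhere the SAP summarises neutrophils, monocytes and lymphocytes (2.8.2), CRP, ferritin and D-dimer by arm and visit (2.7.1), and LDH at baseline (2.3.3).

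**The concern.** The two documents give different instructions for the same samples. A site following Table 8-1 enters the whole panel. A data manager or programmer following SAP 2.8.2 would expect liver tests as values and the rest of the panel only as adverse events.

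The difference matters because the two routes measure different things. A summary of values shows a shift between arms whether or not anyone thought it remarkable. An adverse event appears only after an investigator has judged the value. Under Protocol 10.1.1 an abnormal result counts as an adverse event only if it causes signs or symptoms, is considered clinically significant, or needs therapy. One of the prompts for finding such results is that the value is unusual for the underlying disease. Renal replacement therapy is part of category 7 of the trial's own ordinal scale, so a rising creatinine may be taken as part of the illness and not reported, and practice may differ between sites. For liver tests the SAP avoids this problem with fixed thresholds. It has no equivalent for renal or metabolic results.

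**Working it through.** The plan gives no figure to reproduce here. The check is a count and a comparison of passages.

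**1. Panel size.** Protocol 8.4.1.2 names BUN/urea, creatinine, total bilirubin, direct bilirubin, AST, ALT, ALP, GGT, LDH, sodium, potassium, chloride and calcium (13), and six more: bicarbonate, phosphorus, total protein, albumin, glucose and uric acid. 13 + 6 = 19.

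**2. Named for entry in SAP 2.8.2.** ALT, AST, total bilirubin, direct bilirubin and ALP: 5. Not named: 19 − 5 = 14 (14/19 = 74%).

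**3. Used elsewhere in the readable SAP.** LDH, as a baseline marker in 2.3.3: 1. Remaining: 14 − 1 = 13 (13/19 = 68%). They are BUN/urea, creatinine, GGT, sodium, potassium, chloride, calcium, bicarbonate, phosphorus, total protein, albumin, glucose and uric acid.

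This count is lenient to the SAP. LDH is credited although its readable summary is at baseline only. Direct bilirubin is credited because it is entered, although the listed abnormality criteria use total bilirubin.

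**4. Instructions side by side.**

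| Question | Protocol | SAP 2.8.2 |
|---|---|---|
| Where do chemistry results go? | Clinical database (Table 8-1, section 11.1) | Five liver tests named for entry; clinically significant abnormalities go to adverse events |
| How are they summarised? | By treatment and visit (12.5.3) | Liver tests: counts of new abnormalities and eDISH. Other chemistry: adverse event tables |

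**5. Is the difference declared?** SAP section 4 lists changes to the protocol-specified analyses. Its readable text says nothing about laboratory summaries. Some of its entries are blacked out.

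**6. Samples already planned.** Day -1 (1), Day 2 (1), and the odd days from 3 to 29: (29 − 3)/2 + 1 = 14. That is 1 + 1 + 14 = 16 for a patient in hospital to Day 29, and 17 with Day 57 if still in hospital. Patients discharged earlier have fewer, because phone visits include no laboratory tests.

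**The case against.** A reader might infer that only liver results are entered and that the other 13 analytes are lost. The documents do not support this. SAP 2.8.2 does not use a word of exclusion, and its list cannot be complete for laboratory data as a whole: the SAP itself summarises three blood counts, CRP, ferritin and D-dimer. Even within the chemistry panel it uses LDH, which is not on the list. Protocol 11.1, and the instruction to note unavailable tests on the eCRF, point towards entry. What can be shown is a conflict of instructions and the absence of a planned summary. It cannot be shown that the data were not collected.

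A reader might also infer that creatinine and the rest are never compared between arms. That is too strong. Protocol 10.1.1 asks for review of out-of-range values and of significant changes from baseline, and SAP 2.8.1 tabulates adverse events by treatment, preferred term and severity. The endpoint is worded as participants with clinically significant changes, so the adverse event route does address it in part. It does not supply the summary by treatment and visit that Protocol 12.5.3 promises, and it depends on judgement case by case.

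Two further points stand. SAP section 2.9 and parts of section 4 are redacted, so another laboratory analysis, or a declaration of the change, may exist there. And the emphasis on liver tests and blood counts fits the stated risks: Protocol 4.5 discusses infection and neutropenia, and the special-interest list includes drug-induced liver injury but no renal risk. That explains a choice of emphasis. It does not explain why the protocol's wider promise was left unreconciled.

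**Conclusion.** The conflict is real and should be resolved. Table 8-1 and Protocol 11.1 and 12.5.3 call for the chemistry panel to be recorded and summarised by treatment and visit. SAP 2.8.2 names five liver tests for entry and leaves other chemistry to adverse event reporting. In the readable SAP, 13 of 19 analytes, including creatinine, have no planned comparison of values between arms, and the readable part of section 4 does not declare this.

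The consequence is limited. The safety analyses are descriptive, the primary and key secondary analyses are untouched, and adverse event tables by arm remain. What is missing is a promised safety output and a view of renal and metabolic values that does not depend on who reported them. The documents give no rates of creatinine abnormality and no figure for how many would be reported as adverse events, so the effect on detecting a difference cannot be sized from them. The conclusion rests on the readable text and on the analyte count above.

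**What to change.** Reconcile SAP 2.8.2 with Table 8-1 and Protocol 12.5.3:

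- Keep at least creatinine in the clinical database at every scheduled chemistry sample, and say so in SAP 2.8.2.
- Add to SAP 2.8.2 a summary of creatinine by arm and visit, and the number (%) per arm with newly occurring abnormalities at cut-offs that the sponsor sets before database lock. Multiples of the baseline value are one option.
- List in SAP section 4 any chemistry analyte that will not be summarised. If an analyte is not to be entered at all, Table 8-1 should say so with its source-only code.

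The change needs no new sample or procedure. If the eCRF already holds creatinine, as Protocol 11.1 implies, the cost is SAP text and programming. If not, it is one more local result at each chemistry sample, at most 17 per patient, with the local units and reference ranges needed to make the values comparable.

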## **8.1 Screening**

No rescreening will be permitted.

### **8.1.1 Information to be collected on screening failures**

Participants who sign an informed consent form and subsequently found to be ineligible prior to randomization will be considered a screen failure. The reason for screen failure should be recorded on the appropriate CRF. The demographic information, informed consent, and Inclusion/Exclusion pages must also be completed for screen failure participants. No other data will be entered into the clinical database for participants who are screen failures, unless the participant experienced a serious adverse event during the screening phase (see SAE section for reporting details). If the participant fails to be randomized, the IRT must be notified within 2 days of the screen fail that the participant was not randomized.

Participants who are randomized and fail to start treatment, e.g. participants randomized in error, will be considered an early terminator. The reason for early termination should be recorded on the appropriate CRF.

## **8.2 Participant demographics/other baseline characteristics**

Country-specific regulations should be considered for the collection of demographic and baseline characteristics in alignment with CRF.

Participant race and ethnicity are collected and analyzed to identify variations in safety or efficacy due to these factors as well as to assess the diversity of the study population as required by Health Authorities.

### **8.2.1 Demographic/baseline characteristics information**

[figure not shown]
Demographic data to be collected at screening on all participants include: year of birth or age, gender, race, ethnicity and child-bearing potential (for females only).

Any relevant medical history including date of onset of COVID-19 disease symptoms, date of diagnosis of COVID-19 disease protocol solicited medical history, and/or current medical conditions before obtaining informed consent will be recorded in the Medical History CRF. Significant findings that are observed after the participant has provided informed consent and that meet the definition of an AE must also be recorded in the AE CRF. Whenever possible, diagnoses and not symptoms will be recorded.

Investigators will have the discretion to record abnormal test findings on the medical history CRF whenever in their judgment, the test abnormality occurred prior to the informed consent signature.

### **8.2.2 Prior and concomitant medications**

Relevant prior and concomitant medications will be captured at the screening visit, and updated at the baseline visit. Any changes to the ongoing medications or any new concomitant medications will be recorded in CRF on an ongoing basis throughout study participation.

## 8.3 Efficacy

### 8.3.1 Clinical status (9-point ordinal scale)

[figure not shown]
Assessment of clinical status using a 9-point ordinal scale ([WHO 2020b](#)) will be recorded at baseline on Day 1 before the start of the study treatment and then again once per day through Day 29 of the Study Period, if hospitalized ([Appendix 1](#)). If a patient is discharged from the hospital, the assessment will be made by phone on the visit dates noted in [Table 8-1](#). Each day, the patient's status from the previous calendar day is reviewed; the ordinal score is assigned based on the patient's worst status from the previous day. This score (based on the review of the previous day) will be recorded (i.e. on Day 3, the Day 2 score is determined from review of the previous day's data, and the worst score is recorded as the score for Day 2). In addition, on Day 29 or the Day of discharge, clinical status on Day 29 or the Day of discharge should be recorded.

**Table 8-2 Clinical status (9-point ordinal scale)**

Patient State	Descriptor	Score
Uninfected	No Clinical or virological evidence of infection	0
Ambulatory (not in hospital or in hospital and ready for discharge)	No limitation of activities	1
	Limitation of activities	2
Hospitalized Mild disease	Hospitalized, no oxygen therapy (defined as SpO 2 ≥ 94% on room air)	3
	Oxygen by mask or nasal prongs	4
Hospitalized Severe disease	Non-invasive ventilation or high-flow oxygen	5
	Intubation and mechanical ventilation	6
	Ventilation + additional organ support - pressors, RRT (renal replacement therapy), ECMO (extracorporeal membrane oxygenation)	7
Dead	Death	8

### 8.3.2 Vital signs and oxygen saturation and use

Vital sign measurements include respiratory rate, pulse rate, systolic and diastolic blood pressure, and body temperature. Vital signs should be recorded at a consistent time once each day for a patient (i.e. morning, afternoon or evening) and upon significant clinical changes.

Peripheral oxygen saturation on room air should also be measured at the same time as the vitals, if not on supplemental oxygen. After Day 1, if patient is receiving supplemental oxygen (not on invasive ventilation), then oxygen flow rate (L/min) and/or fraction of inspired oxygen (FiO2) and oxygen saturation should be recorded. PaO2/FiO2 should be recorded as needed.

[REDACTED]

[REDACTED]

[REDACTED]

### 8.3.5 Appropriateness of efficacy assessments

Efficacy endpoints are those employed in other studies of patients with COVID-19 pneumonia ([WHO 2020b](#)).

### 8.4 Safety

Safety assessments are specified below with the assessment schedule detailing when each assessment is to be performed.

For details on AE collection and reporting, refer to AE section ([Section 10.1](#)).

[REDACTED]

#### **8.4.1 Laboratory evaluations**

Clinically significant abnormalities must be recorded as either medical history/current medical conditions or adverse events as appropriate.

##### **8.4.1.1 SARS-CoV-2 virus testing**

For the Screening inclusion criterion, SARS-CoV-2 virus should be measured by PCR or by other approved diagnostic methodology  $\leq 7$  days prior to randomization by local lab. Documentation of the method used should be available in the source notes.

If additional testing is conducted locally, results should be recorded in the CRF.

##### **8.4.1.2 Laboratory evaluations**

Laboratory evaluations will be performed by the local lab.

#### **Hematology**

Hemoglobin, hematocrit, red blood cell count, white blood cell count with differential, and platelet count will be measured according to the assessment schedule in [Table 8-1](#).

